1.2.3.1. Overview of Efficacy in Clinical Studies

In the treatment of pain associated with OA, tanezumab monotherapy doses of 2.5 mg to 10 mg have been shown to provide efficacy that is superior to placebo. In addition, tanezumab monotherapy doses of 5 and 10 mg have demonstrated efficacy above that of NSAIDs. Relative to oxycodone, tanezumab monotherapy doses of 5 mg or 10 mg were shown to have a favorable efficacy profile. Tanezumab 10 mg provided minimal additional benefit over tanezumab 5 mg in the treatment of OA.¹¹

In the treatment of CLBP, tanezumab monotherapy doses of 10 mg and 20 mg demonstrated efficacy that was superior to that of placebo and naproxen. Tanezumab 20 mg provided minimal additional benefit over tanezumab 10 mg in the treatment of CLBP.¹¹

The available efficacy data in other chronic pain conditions suggests that tanezumab may provide meaningful analgesia in subjects with neuropathic pain, visceral pain and subjects with pain associated with cancer who have metastatic bone pain.¹¹

Study A4091056 is a randomized, double-blind, placebo-controlled, multicenter, parallel-group, Phase 3 study of the efficacy and safety of tanezumab when administered by SC injection for 16 weeks compared to placebo in subjects with osteoarthritis of the knee or hip. Approximately 690 subjects will be randomized to one of 3 treatment groups in a 1:1:1 ratio. Subjects will receive a total of two SC injections, separated by 8 weeks:

- tanezumab 2.5 mg (Day 1) and tanezumab 2.5 mg (Week 8);
- tanezumab 2.5 mg (Day 1), and tanezumab 5 mg (Week 8);
- placebo to match tanezumab (Day 1) and placebo to match tanezumab (Week 8).

Study A4091056 is designed with a total duration of 40 weeks and will consist of three periods: Screening (37 days), Double-blind Treatment (16 weeks) and Safety Follow-up (24 weeks).

Study A4091057 is a randomized, double-blind, placebo-controlled, multicenter, parallel-group, Phase 3 study of the efficacy and safety of tanezumab when administered by SC injection for 24 weeks compared to placebo in subjects with osteoarthritis of the knee or hip. Approximately 810 subjects will be randomized to one of 3 treatment groups in a 1:1:1 ratio. Subjects will receive a total of three SC injections, separated by 8 weeks:

- tanezumab 2.5 mg;
- tanezumab 5 mg;
- placebo to match tanezumab.

Study A4091057 is designed with a total duration of 48 weeks and will consist of three periods: Screening (37 days), Double-blind Treatment (24 weeks) and Safety Follow-up (24 weeks).

Study A4091058 is a randomized, double blind, active-controlled, multicenter, parallel-group Phase 3 study of the safety, efficacy, and tolerability of tanezumab when administered by SC injection for 56 weeks compared to NSAIDs in subjects with osteoarthritis of the knee or hip. Approximately 3000 subjects will be randomized to one of 3 treatment groups in a 1:1:1 ratio (N=1000/treatment group). Treatment groups will include:

1. SC placebo (to match tanezumab) once every 8 weeks (a total of 7 administrations) plus naproxen 500 mg BID per os (PO), celecoxib 100 mg BID PO, or diclofenac ER 75 mg BID PO through Week 56.
2. Tanezumab 2.5 mg SC once every 8 weeks (a total of 7 administrations) plus placebo matching naproxen, celecoxib or diclofenac ER to maintain blinded BID oral study treatment administration through Week 56.
3. Tanezumab 5 mg SC once every 8 weeks (a total of 7 administrations) plus placebo matching naproxen, celecoxib or diclofenac ER to maintain blinded BID oral study treatment administration through Week 56.

Study A4091058 is designed with a total duration of 80 weeks and will consist of three periods: Screening (37 days), Double-blind Treatment (56 weeks) and Safety Follow-up (24 weeks).

Study A4091059 is a Phase 3 study of the efficacy and safety of tanezumab in subjects with chronic low back pain, Study A4091061 is a Phase 3 study of the efficacy and safety of tanezumab in cancer patients with pain due to bone metastases. Study A4091063 is a Phase 3 study of the safety and efficacy of tanezumab in Japanese adult subjects with chronic low back pain.

1.2.3.2. Overview of Safety in Clinical Studies

Based on data from all patient populations who have received tanezumab in completed clinical studies to date, the adverse drug reactions listed in Table 2 are considered to be expected in subjects who are treated with tanezumab.

Table 2. Adverse Drug Reactions in All Subjects Receiving Tanezumab

System Organ Class	Adverse Drug Reaction	Frequency ²
Nervous system disorders	Burning sensation Carpal tunnel syndrome Hyperesthesia Hypoesthesia Paraesthesia	Common
	Allodynia Neuropathy peripheral	Uncommon
Musculoskeletal and connective tissue disorders	Rapidly Progressive Osteoarthritis (in patients with underlying osteoarthritis¹)	Uncommon
	Arthralgia Joint swelling Myalgia Pain in extremity	Common
General disorders and administration site conditions	Oedema peripheral	Common

1. Rapidly Progressive Osteoarthritis may occur in subjects with underlying osteoarthritis. The frequency is estimated from adjudicated events of rapidly progressive osteoarthritis in historic clinical studies of tanezumab, which did not include specific risk minimization measures for this adverse reaction.
2. Common ($\geq 1\%$ and $< 10\%$); Uncommon ($\geq 0.1\%$ and $< 1\%$).

The majority of information regarding the safety profile of tanezumab comes from studies conducted in subjects with osteoarthritis. The safety profile observed to date in chronic low back pain and other chronic pain subject populations does not differ markedly from the results observed in the osteoarthritis studies.

A total of 7491 subjects were treated in 9 controlled Phase 3 osteoarthritis studies. The majority of these subjects were treated in studies using IV administration of tanezumab; however, 985 subjects with osteoarthritis were treated in 2 studies using SC administration. The adverse event profile of SC administration of tanezumab is comparable to the IV route. The incidence of adverse events, withdrawals due to adverse events, and serious adverse events in subjects treated with tanezumab monotherapy (5-10 mg) was similar to subjects receiving active comparator treatment and increased over placebo-treated subjects. In the tanezumab 2.5 mg monotherapy treatment group, the incidence of adverse events was similar to active comparator while the incidence of withdrawals due to adverse events, and serious adverse events was similar to that of the placebo treatment group. Across the tanezumab monotherapy doses, the rates of adverse events, withdrawals due to adverse events, and serious adverse events were similar with tanezumab 5 mg and 10 mg, and elevated in comparison to tanezumab 2.5 mg. Tanezumab/NSAID combination therapy was associated with higher overall adverse event rates. The relationship of incidence to the dose of tanezumab administered was similar to that observed with tanezumab monotherapy.

Among the most frequently reported adverse events in the controlled Phase 3 osteoarthritis studies, the incidence of peripheral edema, upper respiratory tract infection, fall, arthralgia, back pain, joint swelling, pain in extremity, hypoesthesia, and paresthesia tended to be higher in patients receiving tanezumab monotherapy than patients receiving either placebo or active comparator treatment. The incidence of peripheral edema, arthralgia, joint swelling, pain in extremity, and paresthesia increased with increasing doses of tanezumab monotherapy. The adverse events with increased incidence observed with active comparator over tanezumab monotherapy included the following: constipation, nausea, urinary tract infection, nasopharyngitis, osteoarthritis, and hypertension.

The most common adverse events reported in the non-controlled, long-term Phase 3 osteoarthritis studies were similar to those seen in the controlled Phase 3 osteoarthritis studies with the exception of the inclusion of musculoskeletal pain and exclusion of hypertension and nasopharyngitis and all gastrointestinal-related adverse events. Dose-related increases in the incidence of peripheral edema, joint swelling, osteoarthritis and paresthesia were observed.

Based on data from the Phase 3 osteoarthritis studies and results of an independent adjudication of investigator-reported adverse events of osteonecrosis and total joint replacements, the risk of rapidly progressive osteoarthritis with tanezumab treatment is greater than with placebo or active comparator treatment.

1.2.3.2.1. Sympathetic Nervous System

In completed Phase 3 osteoarthritis studies, the incidence and discontinuation rates due to adverse events consistent with decreased sympathetic function associated with tanezumab monotherapy (combined doses of 2.5 to 10 mg) were less than or equal to rates with placebo or active comparator. No evidence of dose related elevations in the frequency of adverse events suggestive of decreased sympathetic nervous system function were observed at tanezumab doses of 2.5 to 10 mg in subjects with osteoarthritis or chronic low back pain. Tanezumab 20 mg in chronic low back pain had marginally higher event rates compared to placebo and active comparator treatment groups.

Based on completed osteoarthritis studies where orthostatic blood pressure, heart rate deep breathing, or autonomic symptoms captured with the Neuropathy Symptom Change (NSC) questionnaire were specifically assessed, the data are not suggestive of an adverse effect of tanezumab on autonomic function.

1.2.3.2.2. Joint Safety

Following the imposition of the clinical hold, a comprehensive investigation and analyses related to joint-safety were conducted, based on tanezumab monotherapy exposure in over 6400 subjects and tanezumab/NSAID combination therapy in 3400 subjects. There were over 5000 subjects who received tanezumab treatment alone or in combination with NSAIDs for 6 months or longer. These data were sufficient to define and characterize the adverse event of concern – rapidly progressive osteoarthritis – and evaluate the risk of rapidly progressive osteoarthritis in the context of the overall benefit-risk profile of tanezumab compared to standard of care. The results and conclusions regarding tanezumab and the other anti-NGF therapies are provided in detail elsewhere.^{1,2,3}

After careful investigation no evidence was found to indicate that tanezumab is associated with an increased risk of osteonecrosis, a disease process quite distinct from osteoarthritis. A risk of rapidly progressive osteoarthritis was identified. The risk of rapidly progressive osteoarthritis with tanezumab monotherapy was well below that observed with tanezumab/NSAID combination therapy but greater than with placebo or active comparator treatment. A majority of subjects identified with rapidly progressive osteoarthritis had advanced osteoarthritis of the affected joint prior to treatment. The event rate of all-cause joint replacements in subjects with osteoarthritis was comparable among placebo, active comparator, and tanezumab monotherapy treatment groups.

Risk mitigation measures have been developed as an outgrowth of the joint-related safety analyses to reduce the risk of rapidly progressive osteoarthritis. Risk mitigation measures were developed using recommendations from discussions with European agencies [United Kingdom's Medicines and Healthcare products Regulatory Agency (MHRA), Germany's Paul Ehrlich Institute (PEI) and Spain's Agency on Medicinal Products and Medical Devices (AEMPS)] as well as the FDA Arthritis Advisory Committee and interactions with FDA. These risk mitigation measures have been included in the tanezumab clinical development program.

1.2.4. Rationale for Study

Measures to better characterize the joint safety issue have been developed and agreed with FDA. This study is one component of the agreed risk characterization measures and is an attempt to address the potential concern that subjects treated with tanezumab have a different post-surgical outcome than those not treated with tanezumab. The total joint replacement data from completed tanezumab studies does not suggest a different post-surgical outcome in tanezumab treated subjects however those data were gathered retrospectively. The types of endpoints to be assessed in this prospective study and the duration of the study have been agreed to with the FDA. Every effort will be made to enroll all A4091056, A4091057 and A4091058 subjects who undergo a qualifying total joint replacement into this study however it is acknowledged that to a certain extent the population enrolled in this study will be 'self-selected' and thus there may be subjects with a qualifying total joint replacement who choose not to enter the study.

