2.2. Secondary Objectives

- To compare the post-operative outcome for tanezumab 2.5 mg and 5 mg versus NSAID for subjects who underwent a total knee, hip, or shoulder replacement while participating in tanezumab Study A4091058.
- To describe the post-operative outcome of subjects from the A4091059, A4091061 or A4091063 studies who underwent a total knee, hip, or shoulder replacement.

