5.3. Safety Analysis Set

The ‘Safety Analysis Set’ (SAS) is the analysis set for all analyses. It consists of all treated subjects who enrolled in Study A4091064, and who have a qualifying total joint replacement for Study A4091064. This analysis set is used in the presentations of all data summaries and listings and is labeled as the ‘Safety Analysis Set’ or ‘SAS’.

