5.4. Other Analysis Sets

No other analysis sets are defined.

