8.1.3. Analyses for Binary Endpoints

The incidence of subjects with total joint replacement and specific adjudication outcomes (listed below) will be summarized for all combined osteoarthritis studies. This incidence are shown by treatment group (with a tanezumab combined group, and a total for that parent study). The events to be analyzed are:

- Total Joint Replacement.
- Total Joint Replacement, with outcome adjudicated as:
 - Any of Rapidly Progressive Osteoarthritis (RPOA) type 1 or 2, Subchondral insufficiency fracture (SIF), Primary Osteonecrosis (ON), Pathological Fracture;
 - Any of RPOA type 2, SIF, Primary Osteonecrosis, Pathological Fracture;
 - RPOA type 1 or 2;
 - RPOA type 1;
 - RPOA type 2;
 - ON;
 - Pathological Fracture;
 - SIF;
 - Not enough information to determine rapid or Normal Progression of OA;
 - Normal Progression of OA;
 - Other Joint Outcome.

The analysis will show the number of subjects with the event, the number of subjects in the parent study treatment group (using the ‘Safety Analysis Set’),

An overall summary of subjects with events (total joint replacement and then by adjudication outcome) for all combined osteoarthritis studies and by study will be shown, overall and by treatment group. In addition, two types of summarization, subject level with primary outcome and joint level, will be prepared for adjudicated outcome.

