Post-surgical complications (All OA parent studies)	Any time post-surgery	SAS	None	N/A	Observed	
Concomitant analgesic medication use (All OA parent studies)	Any time post-surgery	SAS	None	N/A	Observed	Summary of surgical outcome
Subpopulation summary of Surgeon's Assessment of Procedural Difficulty for subjects who had RPOA (type 1 and type2), RPOA (type 1), RPOA (type 2), primary ON, SIF, or NPOA	BL, Week 4, 12, 24, 24 (LOCF)	SAS	None	N/A	Observed	Subgroup presentation
Subpopulation summary of Subject's Overall Satisfaction for subjects who had RPOA (type 1 and type2), RPOA (type 1), RPOA (type 2), primary ON, SIF, or NPOA	BL, Week 4, 12, 24, 24 (LOCF)	SAS	None	N/A	Observed	Subgroup presentation

Endpoint	Time points	Analysis Set	Statistical Method	Model/ Covariates/ Strata	Missing Data	Objective
Subpopulation summary of concomitant nondrug treatment for subjects who had RPOA (type 1 and type2), RPOA (type 1), RPOA (type 2), primary ON, SIF, or NPOA	Any time post-surgery	SAS	None	N/A	Observed	Subgroup presentation

SAS: Safety analysis set for subjects with TJR and entered into 1064

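### SAP tables cover only subjects who chose to enter A4091064, so replacement incidence is 100% in every arm by construction and no output shows what fraction of recorded replacements entered

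*Protocol*

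**What the plan says.** **Who is of interest.** The secondary objective in Protocol 2.2 is "To compare the post-operative outcome for tanezumab 2.5 mg and 5 mg versus NSAID". Its target is everyone who had a knee, hip or shoulder replaced during A4091058, not only those who later joined this study.

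**Who is expected to be missing.** Protocol 1.2.4 promises every effort to enrol all qualifying subjects from the three osteoarthritis studies, but accepts that "there may be subjects with a qualifying total joint replacement who choose not to enter the study".

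**Who is analysed.** SAP 5.3 defines the Safety Analysis Set (SAS) for all summaries and listings: "It consists of all treated subjects who enrolled in Study A4091064, and who have a qualifying total joint replacement for Study A4091064". SAP 5.4 adds that "No other analysis sets are defined". Every row of the SAP 8.2.2 table names this set, and its footnote reads "SAS: Safety analysis set for subjects with TJR and entered into 1064". The rows for replacement and adjudication outcomes are included, although their time span covers the parent study as well as A4091064.

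**What was planned for incidence.** Protocol 9.2 plans replacement incidence for all subjects and by A4091058 arm, as percentages and exposure-adjusted rates, with risk differences and ratios against the active comparator and 95% confidence intervals. SAP 8.1.3 keeps an incidence analysis and refers to "the number of subjects in the parent study treatment group", but qualifies this as using the Safety Analysis Set. It does not carry forward the exposure-adjusted rates, risk differences or ratios.

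**The concern.** A set that requires a replacement for membership cannot supply the denominator for a replacement rate. As written, the SAP's incidence rows can describe the mix of adjudicated outcomes among entrants, but not how often replacement, or replacement with a given adjudicated outcome, occurred in each parent arm. That frequency is what Protocol 9.2 asks for.

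The same restriction removes the simplest check on self-selection. If the share of replacement cases that entered differed between the tanezumab and NSAID arms, or if non-entrants had a different mix of joints or adjudicated diagnoses, the planned tables would not show it. The study exists to answer a concern that outcome after surgery differs with tanezumab (Protocol 1.2.4), and SAP Appendix 2 says its data go into a regulatory submission. Readers of the arm comparison will need to know whom it represents.

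**Working it through.** There is no sample-size or power figure to reproduce. Protocol 9.1 gives only an upper guess of fewer than 250 subjects, with unknown distribution across arms.

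**Step 1: incidence on the SAS.** Let n be the SAS members from one parent arm. All n have a qualifying replacement (SAP 5.3), so subject-level incidence is n/n = 100% in every arm, the risk difference is 0 and the risk ratio is 1, whatever happened in the parent study.

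**Step 2: what Protocol 9.2 needs.** Planned sizes in Protocol 1.2.3.1 are 690 (A4091056), 810 (A4091057) and 3000 (A4091058, 1000 per arm), in total 690 + 810 + 3000 = 4500. Taking the ceiling of 250 entrants:

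- 250/4500 = 5.6% of planned subjects.
- If entry is proportional to study size (an assumption), A4091058 supplies 250 × 3000/4500 = 167, or about 56 per arm.
- On a parent-arm denominator, 56 entrants are 56/1000 = 5.6%. On the SAS they are 56/56 = 100%.

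The numerator matters too. Suppose 56 enter from each of two arms, with entry fractions of 90% and 70% (assumed). Recorded replacements are then 56/0.9 = 62 and 56/0.7 = 80, or 6.2% and 8.0% of 1000. Counting entrants only gives 5.6% in both. Replacing the denominator alone would therefore not repair the rows.

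**Step 3: how far non-entry could shift a post-operative comparison.** For one arm, let e be the fraction entering, p the adverse-outcome rate in entrants and q the rate in non-entrants. The rate among all replacement cases is

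e × p + (1 − e) × q.

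The documents give none of e, p or q. Assume p = 10% in both arms, so the observed difference is 0.

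- Same q in both arms, entry 90% versus 70%:
  - q = 20%: 0.9 × 10 + 0.1 × 20 = 11%; 0.7 × 10 + 0.3 × 20 = 13%; hidden difference 2 points.
  - q = 30%: 0.9 × 10 + 0.1 × 30 = 12%; 0.7 × 10 + 0.3 × 30 = 16%; hidden difference 4 points.
- Extreme bounds (q = 0 in one arm and 100% in the other), as tanezumab minus NSAID:

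| Entry, tanezumab / NSAID | Bounds on true difference |
|---|---|
| 95% / 95% | −5 to +5 points |
| 90% / 90% | −10 to +10 points |
| 80% / 80% | −20 to +20 points |
| 70% / 90% | −12 to +28 points |

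**Step 4: set against sampling error.** At 56 per arm and a 10% rate, the 95% half-width for a difference is 1.96 × √(2 × 0.1 × 0.9/56) = 11 points. The 2–4 point shift lies well inside this. The extreme bounds equal or exceed it only when entry falls to about 90% or lower.

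**Step 5: do other planned outputs fill the gap?** SAP 3 plans programme-wide replacement and adjudication summaries, but for the Data Monitoring Committee. SAP 2.1 has replacements in A4091059, A4091061 and A4091063 reported within those studies, which does not bear on the A4091058 comparison. Neither sets entrants against all recorded replacements.

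**The case against.** **Selection on outcome is limited by design.** Protocol 6.1 places consent and Baseline before surgery, and a subject who consents beforehand cannot select on the result. Protocol 5 blinds subjects, investigators and surgeons to parent treatment, and SAP Appendix 2 keeps sites blinded until their subjects finish. This stands in large part. It is not complete: inclusion criterion 3 also admits surgery that has already taken place, and entry could differ by arm with blinding intact if the reason for surgery affects willingness to enter. Protocol 1.2.3.2.2 reports more rapidly progressive osteoarthritis with tanezumab than with placebo or active comparator.

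**SAP 8.1.3 may mean the parent study's own safety set.** The wording allows that reading, and it would give the right denominator. But SAP 5.3, 5.4 and the 8.2.2 footnote leave only one meaning for the term in this document, so the text needs correcting either way.

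**The data exist.** A reader might infer that selection cannot be judged at all. The documents do not support that. Protocol 3 sends all replacement events to adjudication, and the Committee's summaries draw on parent data. The gap is in the SAP's planned outputs, not in what the sponsor holds.

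**The opposite overstatement is also tempting**, namely that every replacement is known. Adjudicating all reported events does not show that all were ascertained. Planned surgery qualifies, Baseline may coincide with the last parent visit, and for subjects refusing follow-up active serious-event reporting ends 112 days after the last subcutaneous dose (Protocol 8.2). A non-entrant's later surgery may go unrecorded.

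**A participation table cannot size the bias, and numbers will be small.** Both stand. Satisfaction, pain and function are not collected in this study on non-entrants. With 56 entrants per arm and 80–90% entry, non-entrants would number 56/0.9 − 56 = 6 to 56/0.8 − 56 = 14 per arm. The SAP dropped age and Kellgren-Lawrence subgroups of the outcome tables for small numbers; a simple count with percentages is still readable at that size.

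**The study is descriptive.** True, so no error rate is affected. The harm is to interpretation.

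**Conclusion.** The point holds, in two parts of different strength.

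The incidence defect is certain and needs no assumption. On the SAS, subject-level replacement incidence is 100% in each arm, so the SAP as written does not deliver the by-arm incidence in Protocol 9.2.

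The missing participation count is a transparency gap. The protocol expects self-selection, and no planned output shows whether entry differed by arm.

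A reader might go further and infer that the tanezumab–NSAID comparison is biased, or that the bias is 2–4 points. The documents support neither. Direction and size are unknown, planned pre-surgery consent and blinding reduce the risk, and the 2–4 points rest wholly on an assumed 10% rate in entrants, 90%/70% entry and 20–30% in non-entrants. The 56 per arm is likewise an assumption, taken from the upper guess of 250.

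**What to change.** 1. In SAP 8.1.3 and the corresponding rows of 8.2.2, replace the SAS for replacement and adjudication incidence. Numerator: all recorded replacements in the parent studies. Denominator: all treated parent-study subjects, by arm. This is what Protocol 9.2 plans. The SAS can stay for the post-operative outcome rows.
2. Add one table by parent study and arm giving recorded qualifying replacements, the number and percent who entered A4091064, and entrants versus non-entrants on joint, age, Kellgren-Lawrence grade and adjudicated outcome where held.
3. Footnote that table: it shows whether entry differed by arm, does not size bias in satisfaction, pain or function, and may miss surgeries after a subject left the parent study.

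No new data collection is needed. The cost is linking to the parent databases and programming one further table.
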